	Standard written patient education at admission to cancer center	Standard written patient education at treatment planning visit	ENROLL/ RANDOMIZE	eSSET-CINV Intervention: 1) Game 2) Decision discussion with research nurse	Standard review of written patient education on side effects	Follow-up phone call
All subjects	x	x	IG	x	x	x
			ACG		x	x

Note: IG= Intervention Group, ACG=Attention Control Group

may act as a distraction, thus reducing anxiety. In addition, patients have already received standard written education regarding treatment effects and will expect CINV as a possible effect of treatment. Written informed consent will be obtained in a private area of the clinic open to the RN. A signed copy of the consent will be given to the patient. Once informed consent is obtained, baseline measures will be completed, and participants will be randomized (Intervention Group [IG] and Attention Control Group [ACG]) to either group by choosing an envelope with a group assignment.

Participants in each group will receive **standard care**: 1) *on admission* to the cancer center (receipt of standard written educational materials that patients are instructed to bring to each appointment), 2) *at a treatment planning visit* (receipt of specific handouts regarding treatment and potential side effects, and 3) *at time of treatment* (verbal review of chemotherapy and symptom handouts by treatment center nurses). See Table 1 for an outline of standard education and eSSET-CINV intervention.

Study Variables

Independent variable: Intervention versus Attention Control group

1) Intervention Group

The intervention will consist of two parts: 1) the eSSET-CINV game and 2) decision discussion with research nurse (RN). The game will be administered by the RN. Participants will play the game at the outpatient treatment center prior to their first chemotherapy treatment using either a study-provided laptop or smart tablet using headphones to ensure privacy and limit distraction. Please see Table 2 for the eSSET-CINV intervention process. At the end of game play, the RN will engage the participant in a discussion about the self-management choices the player made and suggest changes or discuss possible outcomes based on different choices. For example, if the player chose not to treat the avatar's mild nausea and vomiting occurred, the RN would discuss more effective self-management choices as outlined in Figure 3.

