The players will be allowed to play the game as many times as they choose during that chemotherapy visit in order to practice making decisions and visualizing consequences and outcomes. Once the participant is discharged home, a student RA, blinded to the treatment group, will call participants weekly to see how they are doing and remind them to record self-management data. To reduce bias, a scripted interview form will be used. Student RAs will instruct the participant to follow cancer center procedures and call their oncologist if they are having problems or have questions.

Intervention fidelity. eSSET-CINV will be presented and delivered by the same RN each time. The RN will base the discussion on common self-management options (Figure 3). Minor interruptions (< 10 minutes) to game play will be recorded and participants will resume game play where they left off. Technology malfunctions (e.g., system crash or frozen screen) will be recorded and participants will be asked to start eSSET-CINV over. For players with caregivers, caregiver involvement (e.g., helping, prompting) in the game will be recorded for subgroup analysis.

2) Attention Control Group

Participants in the control group will receive: 1) standard care; 2) follow-up phone calls from the student RAs to remind them to record self-management data; and 3) the opportunity to play eSSET:CINV at the end of the study period. During the follow-up phone calls, the student RAs will instruct the participant to follow cancer center procedures and call their oncologist if they are having problems or have questions. Contamination between groups is not expected since participants are likely scheduled for chemotherapy at different times and receiving treatment in different areas of the treatment center.

Co-variates

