Participant characteristics: Demographic and experiential characteristics that may influence CINV and ability to self-manage this symptom will be measured at T1 (baseline). Demographics include: age, gender, comorbidity information, education level, and income level. Experiential characteristics include: cancer diagnosis and stage, chemotherapy regimen with antiemetics, discharge antiemetic prescriptions, use of the Internet to research symptom management information, and caregiver presence (yes/no) and involvement at home. All cancer information will be collected from the patient's electronic medical record by the RN. Delays in chemotherapy treatment and rationale for delay will also be recorded at each time point by the RN.

Dependent Variables

An overview of study variables, measures and data collection timeline are presented in Table 3. Data will be collected for 4 treatment cycles (3 or 4 months depending on cycle length). Questionnaires will use a paper/pencil format with enlarged font and be entered into Excel™ software.

1) Symptom severity: The *Symptom Representation Questionnaire (SRQ)*⁹¹, a 24-item self-report measure will be used to identify presence and severity of common treatment-related symptoms (0-10 Likert scale), including nausea and vomiting (N/V). This measure asks respondents to think about their symptoms over the past week.

Table 2: eSSET-CINV Intervention process

1	Game introduction and orientation
2	Choose avatar
3	Avatar discharged home after treatment
4	Avatar begins to experience nausea
5	Player makes self-management decisions
6	Avatar responds based on player decisions
7	Avatar experience continues with periodic nausea as player continues to make self-management decisions
8	Game ends when avatar achieves goal of mild or no nausea or has an unplanned ED or hospital admission
9	Discussion of decision choices with Research Nurse

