of self-management strategies used and, 3) the strategies *perceived helpfulness* in reducing nausea (0-10 Likert scale). Preventative self-management activities for CINV will also be recorded. All self-management strategies are coded (e.g., “MED”= taking antiemetic, “DIS”- using distraction), and the participants will fill in the strategy code they are using on the form. To lessen the risk of the SMC becoming an intervention for the Control Group, all participants will be asked to record self-management behaviors of other common treatment-related symptoms (i.e. fatigue, mouth/throat sores). The SMC will be collected by the research nurse at chemotherapy cycles 2, 3 and 4.

4) Health-related Quality of Life- The EORTC-30⁹² will measure QOL at each treatment cycle. This frequency is consistent with others studies that have measured QOL in older adults over time.^{59, 93} This well-known scale includes 5 functional scales, 3 symptom scales, and 6 single items using a 4-point Likert scale (“not at all” to “very much”), and 2 global health/QOL items using a 7-point Likert scale (“very poor” to “excellent”). Higher scores on the functional and health/QOL scale indicate better functioning, while higher scores on the symptom-related scales and items indicate higher symptoms. Reliabilities (Cronbach's alphas) range from 0.52 (role functioning scale) to 0.89 (QOL).⁹²

5) Resource Use: Any unplanned Emergency Department or hospital admission will be recorded via participant report using a dichotomous (Y/N) variable at each follow-up phone contact and treatment visit. Follow-up questions about the reason for the admission, length of time for admission and treatment will also be asked. The report will be verified by medical record review whenever possible.

Additional Outcomes:

Game appeal: Under the guidance of the PI, student RAs will develop and pre-test a short survey to evaluate game appeal at the first follow-up phone call. Using a 4-point agreement scale, participants will be asked the extent to which they agree or disagree with statements regarding ease of game play, game likability, clarity of self-management choices, usefulness in educating about CINV consequences and ability to be controlled/cured, and realism (setting and scenario). Additional comments about the game will be recorded.

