Willingness to recommend the game will be assessed using one item: Would you recommend this game to other older adults about to start chemotherapy treatment (yes/no)? This will be collected at Cycle 4 (T4).

Table 3: Summary of dependent variables, measures and data collection time points

		Data Collection Time points			
Dependent Variable/Outcome s	Measure	T1 Baseline	T2 Cycle 2	T3 Cycle 3	T4 Cycle 4
Symptom severity	SRQ- patient report	x	x	x	x
Cognitive representation	SRQ-patient report	x	x	x	x
Self-management behaviors*	SMC- patient report		x	x	x
Resource Use	Patient report		x	x	x
QOL	EORTC-patient report	x	x	x	x

*Note: self-management behaviors will be recorded daily by participants, but collected by the research nurse at each treatment visit

DATA ANALYSIS

Phase I: Game prototype and production

AIM 1: Identify real-life scenarios involving CINV incidence, self-management, and consequences using a peer Community Advisory Board of older adults who have undergone cancer treatment, their family members, and oncology nurses to design and develop a serious game for CINV self-care decision making.

AIM 2: Identify design aspects and elements of eSSET-CINV game play, audio, and visual avatar development that have the greatest appeal for older adults with cancer.

Data from focus groups will be digitally audio-recorded and transcribed. Methods consistent with classic content analysis will be used to analyze data from the focus groups and will begin immediately after each focus group.⁹⁴ The focus group recordings will be reviewed by the PI and student RAs and content analysis will be conducted to thematically categorize responses. Data will be de-identified in analysis-no names will be used. In order to eliminate bias, the analysis will remain grounded in the data. Themes will be created and coded using language similar to what the participants use. These codes will then be grouped by similarity and used to summarize feedback about the game and suggestions for improvement.⁹⁴ The notes taken by the RAs during and after the focus groups will serve as a “trail of evidence” to increase the trustworthiness of the data and confirm final findings. Data are not intended to be generalized but will answer specific study AIMS.

Phase II: Game prototype testing

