Preliminary data analysis: Descriptive statistics will be provided to characterize the study participants for all demographic and experiential variables at baseline and at each treatment cycle time point. Summary tables will be provided to present participant characteristics (e.g., gender, age group, race), major study variables, game appeal, and willingness to recommend game to others. Internal consistency of study measures will be checked and evaluated to ensure data quality. Effort will be taken as much as possible to avoid missing data. If there are significant missing data that may impact analysis results, the multiple imputation method may be used for the analysis of primary endpoint. All statistical analyses will be performed using Statistical Application Packages (SAS®), version 9.4.

Principle data analysis: The primary endpoints for the study are N/V severity score and the number of self-management behaviors. The secondary endpoints are ED/hospital admission and QOL. Summary statistics for the primary and secondary endpoints will be provided. The t-test will be used if the normality of the endpoint can be confirmed. Otherwise, the Wilcoxon Rank-Sum test will be used to assess the difference between the two groups at each treatment cycle time point.

AIM 1: Estimate effect size of the eSSET-CINV in changing patient outcomes: cognitive representation, self-management behaviors, CINV severity, QOL, and resource use. The effect size of N/V severity score will be estimated using the Cohen’s d, which is defined as the difference between two means divided by a standard deviation for the data.

AIM 2: Examine differences in cognitive representation, self-management behaviors, CINV severity, QOL, and resource use, between, and within, the intervention and attention control groups. For the primary endpoints, the data will be collected over 4 treatment cycles, and the method of analysis of longitudinal data will be used to compare the difference between intervention and control groups over time. The generalized estimating equation (GEE) approach may be used to enhance the robustness of the estimation of model parameters when the ideal working correlation structure is difficult to pre-specify. In the longitudinal model treatment cycle time, interaction of time and treatment, or both, whenever feasible, may be added into the model to assess the time effect on treatment difference.

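### ED and hospital admissions are found through participant report, with the record used only to verify that report, so admissions that go unreported can be missed

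*Combined protocol and SAP*

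**What the plan says.** The Principle data analysis section sets the status of the outcome: "The secondary endpoints are ED/hospital admission and QOL." Resource use is also named in Phase II Aims 1 and 2.

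Under Dependent Variables, item 5 (Resource Use), any unplanned ED or hospital admission "will be recorded via participant report using a dichotomous (Y/N) variable at each follow-up phone contact and treatment visit." Follow-up questions cover the reason, duration and treatment. The item then says: "The report will be verified by medical record review whenever possible." Table 3 gives the measure for Resource Use as "patient report" at T2, T3 and T4, and names no second source.

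Other sections bear on how well this works:

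- **Caller.** Study Variables, Intervention Group: "a student RA, blinded to the treatment group, will call participants weekly to see how they are doing." The interview form is scripted.
- **Record access.** The research nurse screens for eligibility in the electronic record (Recruitment and randomization). Under Co-variates, "All cancer information will be collected from the patient's electronic medical record by the RN." The nurse also logs chemotherapy delays and their reasons at each time point.
- **Participants' awareness of their arm.** In the intervention arm, "Participants will play the game at the outpatient treatment center prior to their first chemotherapy treatment." Controls get "the opportunity to play eSSET:CINV at the end of the study period."
- **Attrition and missing data.** Enrolment allows 20% for attrition. The only missing-data method, optional multiple imputation, is mentioned for the primary endpoint alone.

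**The concern.** A participant who is ill, in hospital, out of contact or withdrawn may give no report, and then there is nothing to verify. Some of these reasons for silence are linked to the outcome itself, so the admissions most likely to go unrecorded may be those of the sickest participants.

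Fewer unplanned admissions is one of the benefits claimed for the game in the Significance section, and Phase II exists to estimate effect sizes. An incomplete count lowers the observed admission rate in both arms, and that rate would feed into planning of a later trial. If completeness also differed by arm, the estimated effect itself would be distorted.

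**Working it through.** The plan has no figure to reproduce here: it gives no admission rate, no reporting sensitivity and no sample size for secondary endpoints. The main check is therefore of the text, followed by an illustration on assumed values.

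**Step 1. Trace each route by which an admission could enter the data.**

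- *Phone contact or treatment visit:* stated, and requires the participant to report.
- *Record review:* stated, but its object is the report, and only where possible.
- *Delay log:* covers every participant under treatment and may show an admission that held up a cycle. The plan does not use it to identify events, and an ED visit need not delay a cycle.
- *Caregiver or proxy report, or a record search of all participants:* not provided for in any section.
- *Rule for missed contacts, dropout or death:* none for this endpoint.

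Participant report is therefore the only stated route to an event.

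**Step 2. Equal under-reporting (assumed values).** Let r be the true risk in both arms and s the share of admitted participants whose admission is captured. Expected loss among 66 = 66 × r × (1 − s).

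- r = 0.15, s = 0.90: 66 × 0.15 × 0.10 = 1.0
- r = 0.25, s = 0.80: 66 × 0.25 × 0.20 = 3.3
- r = 0.35, s = 0.70: 66 × 0.35 × 0.30 = 6.9

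In an arm of 33, each lost event moves the observed rate by 1/33 = 3.0 percentage points.

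**Step 3. Unequal under-reporting with no true effect (assumed values).** Observed risk = r × s, so the observed risk ratio is the ratio of the two capture shares.

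- 70% in the intervention arm, 90% in control: 0.70/0.90 = 0.78
- The reverse: 0.90/0.70 = 1.29
- Absolute gap: 0.20 × r, which is 3 points at r = 0.15, 5 points at 0.25 and 7 points at 0.35

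**Step 4. With a true effect (assumed 30% control, 15% intervention).**

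- 80% capture in both arms: 24% versus 12%. The risk ratio stays at 0.50, but the difference shrinks from 15 to 12 points. Power at 33 per arm falls from about 31% to 24% (normal approximation, two-sided 5%, also assumed because the plan states no alpha).
- 70% capture in control and 90% in intervention: 0.30 × 0.70 = 21.0% versus 0.15 × 0.90 = 13.5%, so the risk ratio is 0.135/0.210 = 0.64 and power is about 12%.

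Steps 2 to 4 show how the error behaves. They do not estimate what this trial will lose.

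**The case against.** The strongest reply is that the plan asks often and asks well. An ED visit or admission is a discrete, memorable event. Participants are asked weekly by a blinded caller with a script, and again at each treatment visit, so a stay missed at one call can be reported at the next. The delay log may reveal others. This stands. It rules out saying that admissions will be missed as a matter of course, and leaves the risk mainly with participants who stay unreachable, drop out or do not report.

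The verification sentence is also open to a wider reading. The report is a yes/no answer, so checking it could include checking a no. If that is the intent, one sentence would settle it, but it would still not reach people who gave no report.

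Three stronger inferences are tempting but not supported:

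- **That non-contact is counted as no admission.** No section says how non-contact is coded.
- **That reporting is biased by arm.** Participants can hardly avoid knowing whether they played the game, and the game can end in an unplanned admission. That could make them more or less ready to report, and the documents support neither direction. The blinded caller limits interviewer bias but not what participants choose to disclose.
- **That this is a failure of safety monitoring.** The documents call the outcome resource use and treat it as an outcome of an educational intervention.

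Sampling error is also larger than the illustrated bias. With observed risks of 17.5% and 22.5% at 33 per arm, the standard error of the difference is √[(0.175 × 0.825 + 0.225 × 0.775)/33] = 0.098. The false 5-point gap is about half of that.

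**Conclusion.** The ascertainment rule has a real gap. ED/hospital admission rests on participant report, the record is described only as verifying that report, and no section covers participants who do not report, stay unreachable or drop out. Their admissions can be missed, although repeated questioning and the delay log will recover some.

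The size of the loss is unknown. The range of about 1 to 7 admissions among 66 rests wholly on an assumed true risk of 15% to 35% and assumed capture of 70% to 90%. The risk ratios of 0.78 and 1.29 further assume a difference in capture between arms that nothing in the documents demonstrates. A reader might infer that the group comparison is already biased, but that would go too far. What is established is incomplete capture as a possibility, on a secondary endpoint, with a better source already open to the study team. This is a worthwhile, inexpensive improvement. It is not a defect that invalidates the trial.

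**What to change.** Amend the Resource Use item and Table 3 as follows:

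1. **Search everyone.** Search the electronic record for ED visits and hospital admissions for every randomised participant in both arms, whatever was reported. Define the window in the same way for all, from first treatment to the planned T4 date, so that it does not end early for those who drop out.
2. **Standardise the classification.** Use a fixed extraction form and a pre-set rule for what counts as unplanned. Because the research nurse delivers the intervention and knows the arm, existing staff blinded to arm should classify events where feasible.
3. **Combine the sources.** Count an event once if either source shows it, and flag the source. Keep the phone and visit questions, since the record may not show admissions to outside hospitals.
4. **Report what remains unknown.** Present deaths and loss of contact by arm beside the endpoint.

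The cost is revised protocol wording, a little record-review time per participant, and a check that the consent and privacy wording covers the search. Blinded classification may take some time from a second member of staff.

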Setting: The outpatient treatment center at the UF Health Cancer Center-Orlando will be the primary site for enrollment due to its long-standing relationship with these researchers. In 2013, UF Health Cancer Center-Orlando saw approximately 4,694 patients. Of these 2,573 patients were age 65 or older, and 565 of these patients received outpatient chemotherapy. These numbers indicate an ample sampling pool of older adults.

Sample size: The target sample is older adults receiving emetogenic chemotherapy for the first time. Sixty-six participants will be enrolled if they meet the following **inclusion criteria**: age 65 and older, newly diagnosed with any cancer, treatment with any chemotherapeutic agent with a moderate to severe emetic potential (on a 3- or 4- week cycle), proficient in English, and have a telephone. **Exclusion criteria** include: previous diagnosis and treatment for cancer, advanced or end stage disease with a palliative intent, visually or hearing impaired. Dementia or cognitive impairment is not a concern with the population since they have already been cognitively screened in order to consent to treatment at this cancer center. There will be no exclusion based on gender or racial/ethnic status. Retention of all participants will be enhanced by the following strategies 1) weekly telephone follow-up phone calls by the RA; 2) a \$50 incentive/gift card at the end of the study period; and 3) attention control group offered eSSET-CINV at the end of the study. We will oversample by 20% in order to account for attrition.

Phase II Procedures:

Recruitment and randomization: Successful recruitment and retention strategies previously established by the team will be used during this phase.^{7, 15, 16, 18, 90} Convenience sampling, followed by randomization will be used. All new patients will be screened for eligibility by the Research Nurse (RN-PG) using the Sunrise XA -

electronic medical record system used by Orlando Health. Eligible patients will be approached by the RN at their first chemotherapy appointment and asked to participate. This timing is not expected to add to or create patient anxiety. Patients usually wait 30 to 60 minutes for lab results and chemotherapy to be delivered. Participating

Table 1: Intervention schema

	Pre-treatment		First Treatment Visit			Post - treatment

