The one-way repeated measures ANOVA will be used to assess the difference between the two groups. The mixed effect model may be used as exploratory analysis to account for unobservable variations from each individual patient. In addition, comparisons between two groups at each treatment cycle time point will be performed for all primary and secondary endpoints. For this particular comparison, the univariate normality of each endpoint will be assessed graphically at each treatment cycle time point. An appropriate time window will be determined to define the treatment cycles for the study.

AIM 3: Obtain preliminary data regarding the feasibility and acceptability of the game in older adults experiencing CINV. Feasibility- Computer science and digital media undergraduate students will work under the direction of [name] and [name] to identify patterns in game play data (e.g., self-management decisions, scenario patterns of progression), time to game completion, and number of times the game was played (intervention dose). The RN will track any instance of game play interruptions or

malfuction. This data will be summarized with descriptive statistics. **Game Appeal:** Responses to the game appeal and willingness to recommend questions will be scored and summed using descriptive statistics. Additional comments about the game will be recorded and analyzed for themes.

Sample size and statistical power:

Based on the assumption of a nausea severity mean score of 6.20, range from 2 to 9, a standard deviation of 2.44, and a clinically meaningful difference in mean nausea severity score of one between the intervention and control groups, with 90% power, the required sample size is 33 participants for each group, yielding a total sample size of 66 for the study. To reduce the patient selection bias, single-blinded randomization may be used whenever feasible. Due to lack of available data from prior research the sample size for secondary endpoints is not possible for the study at first stage. However, the power statistical analysis will be assessed when data become available from the planned study.

Potential challenges and strategies for addressing:

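### The named analyses the plan commits to leave out patients with missing visits, while the methods that could handle severity-related dropout are optional, unspecified or exploratory

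*Combined protocol and SAP*

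**What the plan says.** The Phase II section on sample size sets the allowance: "We will oversample by 20% in order to account for attrition". Severity is measured at baseline (T1) and at cycles 2, 3 and 4 (T2 to T4, Table 3). The paragraph headed Principle data analysis names two primary endpoints, N/V severity and the number of self-management behaviors.

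Sorted by strength of commitment, the Phase II analyses are:

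- **Committed and named:** a t-test or Wilcoxon test between groups at each cycle (Principle data analysis, repeated under AIM 2), and a one-way repeated measures ANOVA (AIM 2).
- **Committed but not named:** a longitudinal comparison of the groups over time (AIM 2).
- **Optional:** "The generalized estimating equation (GEE) approach may be used to enhance the robustness of the estimation of model parameters", offered for when the working correlation is hard to choose, with no weighting for missing data; and, under Preliminary data analysis, "If there are significant missing data that may impact analysis results, the multiple imputation method may be used for the analysis of primary endpoint".
- **Exploratory:** "The mixed effect model may be used as exploratory analysis to account for unobservable variations from each individual patient".

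The plan gives no analysis set, no threshold for the imputation trigger, no imputation model, no assumed missing-data mechanism and no sensitivity analysis. The imputation sentence speaks of one primary endpoint, although there are two.

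**The concern.** A per-cycle test drops anyone without a value at that cycle. Repeated measures ANOVA in its usual form drops anyone missing any cycle. Unweighted GEE generally needs data missing completely at random; its robustness to a wrong working correlation does not extend to informative dropout. Two listed methods remain valid when dropout depends on severity already recorded: a likelihood mixed model, and multiple imputation with a suitable model. The plan commits to neither.

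The plan's own text makes severity-related loss plausible. Section A lists non-adherence with treatment among the effects of nausea and vomiting, and T2 to T4 data are collected at treatment visits, so a patient who stops coming for treatment is likely to lose later outcomes. The intervention aims to reduce that same symptom, so loss could also differ between arms.

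At stake is the main product of the trial: Phase II AIM 1 is to estimate an effect size. The open imputation trigger also leaves a choice that could be made after the data are seen.

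**Working it through.** **1. The plan's figures.** The missing-data text contains no figure to reproduce. The scale comes from the section on sample size and statistical power: "a clinically meaningful difference in mean nausea severity score of one between the intervention and control groups", with "a standard deviation of 2.44". That section's 33 per group does not follow from these inputs. Assuming two-sided alpha 0.05 (none is stated), n = 2 × (1.960 + 1.282)² × 2.44² / 1² ≈ 125.1, so 126 per arm. That is a separate matter; only the difference and SD are used below.

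**2. What 20% means.** Enrolling N × 1.2 covers a loss of 1 − 1/1.2 = 16.7%; enrolling N/0.8 covers 20%. I use 20% as a round value.

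**3. Same dropout mechanism in both arms.** From the plan: true difference −1 at T2 to T4, SD 2.44. Assumed: correlation 0.6 between visits, and logit P(dropout after visit k) = a + b × severity at visit k, for k = T2 and T3, with a set so that total dropout is 20%. The slope b runs from 0.2 to 0.8 per point. Per SD these are odds ratios of exp(0.2 × 2.44) = 1.6 to exp(0.8 × 2.44) = 7.0. Simulation with 400,000 per arm gives:

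| Slope b | T4, patients seen | Completers, mean of T2–T4 |
|---|---|---|
| 0.2 | −0.97 | −0.96 |
| 0.4 | −0.92 | −0.90 |
| 0.6 | −0.87 | −0.84 |
| 0.8 | −0.83 | −0.79 |

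The completers' column is what a complete-data ANOVA would estimate. The loss is 1 − 0.96 = 4% to 1 − 0.79 = 21%, or roughly 4% to 20% given simulation error of about 0.01. A repeat with 1,500,000 per arm agreed to about 0.01. In that repeat, dropout at slope 0.8 was about 25% of controls and 15% of the intervention arm, although one rule applied to both. An estimator valid under missing at random (T4 regressed on earlier severity within arm, then averaged over everyone) returned −0.99 to −1.00.

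**4. Other mechanisms.** Here dropout of about 20% before T4 depends on T2 severity, except in the last row, with log-odds 1 per SD (1/2.44 = 0.41 per point) and correlation 0.3 to 0.7:

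| Dropout | T4, patients seen |
|---|---|
| Unrelated to severity | −1.00 (within about 0.01) |
| Severity-driven, same in both arms | −0.96 to −0.92 |
| Severity-driven in control only | −0.86 to −0.70 |
| Severity-driven in intervention only | −1.13 to −1.30 |
| Opposite directions in the two arms | −0.74 to −0.42 |
| Driven by the unseen T4 value, both arms | −0.89 |

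The estimator valid under missing at random gave −0.99 to −1.01 in all the rows driven by T2 severity. In the last row it gave only −0.90 to −0.94, so most of that bias remains.

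**5. Against sampling error.** With 26 per arm (33 × 0.8 ≈ 26), the standard error of a one-visit difference is 2.44 × √(2/26) = 0.68. The largest T4 bias in step 3, 0.17, is 0.17/0.68 = one quarter of it.

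**The case against.** Much can be said for the plan. It does list multiple imputation for the primary endpoint, and it does commit to a longitudinal analysis that could turn out to be likelihood-based. It takes retention seriously, with weekly calls, a gift card and later access to the game for controls, and it records treatment delays and their reasons. At moderate slopes the bias is a few percent, and even the worst T4 figure in the common-mechanism case is small beside the sampling error of a trial this size. The simulation in step 3 also favors the remedy, because dropout there depends only on observed values.

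All of this stands, and it limits the point. It does not remove it. An unnamed method and an optional, unspecified imputation commit the sponsor to nothing. A confidence interval reflects sampling error but not dropout bias.

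A reader might infer four stronger things that the documents do not support:

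- **That dropout will bias the result, or will shrink it.** No passage says severe nausea causes loss from the study; the link to non-adherence makes it plausible only. If the mechanism differs by arm, the effect can be exaggerated.
- **That 20% attrition is forecast.** The plan gives an oversampling allowance.
- **That imputation will be decided with the results in view.** The timing is not stated, and the amount of missing data can be judged without comparing arms. This is an open risk.
- **That the mixed model is the only valid method listed.** Properly specified multiple imputation is valid under the same assumption.

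**Conclusion.** The point holds in conditional form. The plan makes an allowance for attrition but commits to no named method that stays valid when dropout depends on earlier severity. If such dropout occurs by one mechanism in both arms, the analyses it does name can lose roughly 4% to 20% of a one-point effect. The upper end needs odds of dropout that rise about sevenfold per SD of severity. The correlation, slopes and dropout rate are assumptions; the SD and target difference are the plan's. This does not invalidate the trial, but it is an avoidable weakness in a study whose first Phase II aim is an effect estimate, and it should be corrected in the SAP.

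**What to change.** In the Phase II Data Analysis text:

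1. Make one likelihood-based longitudinal model, using all observed visits of all randomized patients, the main analysis of N/V severity whatever the amount of missing data. Include the T1 value in the model so that patients lost before T2 contribute. They will add little if severity before chemotherapy predicts later severity only weakly.
2. Use a corresponding model for the number of self-management behaviors, for example a count mixed model or multiple imputation with a stated model. Table 3 has no T1 value for this endpoint, so patients lost before T2 can enter only through baseline covariates in an imputation model.
3. Make the per-cycle t-test or Wilcoxon results, the repeated measures ANOVA and GEE supportive.
4. Replace the conditional imputation sentence with a fixed sensitivity analysis that allows dropout to depend on unseen values, for example delta-adjusted multiple imputation with the range of deltas set in advance. The likelihood model does not remove that bias.
5. Define the analysis set.

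The cost is SAP wording and slightly more analysis work, with no new data; the plan already specifies SAS 9.4. The main analysis would then rest on a missing-at-random assumption, which is why item 4 is needed.
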